11.2. Data management

Data management will be outsourced to a Contract Research Organization (CRO). The data managers will issue electronic edit checks via EDC, and modification of the data will be permitted by the investigator to achieve accuracy with source documents and eliminate all inconsistencies in the data.

The data will be reviewed for completeness and logical consistency. Automated validation programs will identify missing data, out of range data and other data inconsistencies at the time of entry.

All new/updated information will be reviewed and verified by the appointed monitor.

11.3. Data coding

Adverse events, concomitant diseases, medical/surgical histories will be coded using the Medical Dictionary for Regulatory Activities (MedDRA). Concomitant medication will be coded using the WHO-DRUG dictionary.

11.4. Study Monitoring

The study will be conducted in accordance with the ICH Note for Guidance on GCP (ICH, Topic 6, 1996). The appointed monitor will contact the site prior to the start of the study to review with the site staff the protocol, study requirements, and their responsibilities to satisfy regulatory, ethical, and ABIVAX requirements. Throughout the study, the monitor will arrange visits to the study center at appropriate intervals to assess the progress of the study and review the completed eCRFs.

During the monitoring visits, the monitor will:

- Ensure that the safety and the rights of subjects are being protected;
- Check that the data are authentic, accurate, and complete and discuss any inconsistencies;
- Ensure that all study materials are correctly stored and dispensed with particular emphasis to the investigational product;
- Verify that the site staff and facilities continue to be adequate for the proper conduct of the study;
- Ensure that the study is conducted in accordance with the currently approved protocol and any other study agreements, GCP, and all applicable regulatory requirements;
- Help resolve any problems that may have arisen.

In line with ICH GCP guidelines, monitoring will include verification of data entered in the CRF against the original

subject records. Therefore, for the purpose of monitoring review, direct access to all study-related site and source documents is mandatory. Data items for which the eCRF will serve as the source document will be identified, agreed upon and documented. The investigator must also ensure provision of sufficient time, space and qualified personnel for the monitoring visits.

11.5. Records Retention

Following closure of the study, the investigator or the head of the medical institution (where applicable) must maintain all site study records, except for those required by local regulations to be maintained by someone else, in a safe and secure location. The records must be maintained to allow easy and timely retrieval, when needed (e.g., audit or inspection), and, whenever feasible, to allow any subsequent review of data in conjunction with assessment of the facility, supporting systems, and staff.

ABIVAX will inform the investigator/institution of the required time period for retaining these records in order to be compliant with all applicable regulatory requirements. The minimum retention time will meet the strictest standard applicable to that study site, as dictated by ICH GCP E6 Section 4.9, any institutional requirements or local laws and regulations, or ABIVAX standards/procedures; otherwise, by default the retention period will be 25 years.

The investigator must notify ABIVAX of any changes in the archival arrangements, including, but not limited to, the following: archival at an off-site facility, transfer of ownership of the records in the event the investigator leaves the site. In addition, the investigator should seek the written approval of the Sponsor prior to disposing any of the archived records.

11.6. Quality Assurance and Inspection by Authorities

To ensure compliance with GCP and all applicable regulatory requirements, ABIVAX may conduct quality assurance audits. Regulatory agencies may also conduct a regulatory inspection of this study. Such audits/inspections can occur at any time during or after completion of the study. By signing the protocol agreement page, the investigator agrees to permit drug regulatory agencies and ABIVAX audits. If an audit or inspection occurs, the investigator and institution will allow the auditor/inspector direct access to all relevant documents and to allocate his/her time and the time of his/her staff to the auditor/inspector to discuss findings and any relevant issues. Items of particular interest in case of an audit are, but not limited to, the following:

- IRB/IEC and regulatory authority approvals;
- Informed consent forms of the subjects;
- Approved study protocol and amendments and investigator brochure;
- Treatment accountability;
- Safety reporting;
- Study file;
- Study personnel;
- Log of monitoring visits and monitoring process;
- Medical records and other source documents;
- Site facilities;
- Reports to the IRB/IEC and the sponsor;
- Record retention.

11.7. Study and Site Closure

If the study is terminated prematurely or suspended for any reason, the investigator/institution should promptly inform the study subjects and should assure appropriate therapy and follow-up for the subjects.

ABIVAX reserves the right to temporarily suspend or prematurely discontinue this study, at any time for reasons including, but not limited to, safety or ethical issues or severe non-compliance. For multicenter studies, this can occur at one or more or at all sites. If such action is required, the Sponsor will discuss this with the investigator or the head of the medical institution (where applicable), including the reasons for taking such action, at that time. Advance notification will be provided to the site(s) when feasible, on the impending action prior to it taking effect.

All investigators and/or medical institutions conducting the study will be informed in writing should the Sponsor decide to suspend or prematurely discontinue the study for safety reasons. The regulatory authorities will also be informed of the suspension or premature discontinuation of the study and the reason(s) for the action. If required by local regulations, the investigator must inform the IRB/IEC promptly and provide the reason for the suspension or premature discontinuation.

Upon premature discontinuation of the study, the monitor will conduct site closure activities with the investigator or site staff, as appropriate, in accordance with applicable regulations, GCP, and ABIVAX procedures. All data must be returned to ABIVAX. Arrangements will be made for any unused investigational product based on the relevant ABIVAX procedures for the study.

11.8. Study report and Publication

Upon conclusion of the study, an integrated clinical and statistical study report will be written by the Sponsor in consultation with the Coordinating Investigator. This report will be based on the items detailed in this study protocol. When the clinical study report is completed, ABIVAX will provide the investigators with a full summary of the study results. The investigators are encouraged to share the summary results with the subjects, as appropriate.

The first resulting publication will be a full publication of all data from all participating sites, coordinated by ABIVAX. Any secondary publications by the investigators (abstracts in journals, oral presentations etc.) will reference the original publication and will require pre-submission review by the Sponsor. Note that the Sponsor is entitled to delay any proposed secondary publication, in order to obtain patent protection, if required.

The Coordinating Investigator as well as other members of the study committee will be authors on the first publication. The principal investigator of the trial will be the first author. Authorship for other investigators will be assigned on the basis of their recruitment contribution, as well as intellectual and administrative input. Ranking will be according to the number of subjects randomized as well as contribution to the study conduct and preparation of final manuscript.

11.9. Ownership and Confidentiality

All information provided by ABIVAX and all data and information generated by the sites, as parts of the study (excluding the subjects' medical records) are property of ABIVAX.

All potential investigators must be aware of and agree in writing (confidentiality agreement) to the confidential nature of the information pertaining to this study. Furthermore, all information provided by ABIVAX and all data and information generated by the sites during the study must be kept confidential by the investigator and other site staff, and may not be used for any purpose other than conducting this study.

13. APPENDICES

Appendix 1: Division of AIDS table for grading the severity of adult and pediatric adverse events

The severity of adverse events will be assessed using the division of AIDS table for grading the severity of adult and pediatric adverse events, version 2.0 of November 2014. A copy can be downloaded from the internet web site below or supplied upon request to ABIVAX:

http://rsc.tech-res.com/Document/safetyandpharmacovigilance/DAIDS_AE_Grading_Table_v2_NOV2014.pdf

Appendix 2: CYPIA2 substrates or inducers (in bold: prohibited concomitant medications)

Amitriptyline, Clomipramine, Imipramine, Agomelatine, Fluvoxamine, **Clozapine**, Olanzapine, Haloperidol, Ropivacaine, **Theophylline**, Zolmitriptan, Tamoxifen, Erlotinib, Cyclobenzaprine, Mexiletine, Naproxen, Ondansetron, Phenacetin, Paracetamol, Propranolol, Tacrine, Tizanidine, Verapamil, **Warfarin**, Zileuton, **Ropinirole**, **Methadone**

Appendix 3: Standard operating procedures for laboratory analyses

Cf. Lab Manual

## 1 Introduction

This document outlines the Statistical Analysis Plan (SAP) for the ABIVAX sponsored ABX464. PHASE Ib, STUDY CODE: ABX464-005.

## 2 Study Objectives

### 2.1 Primary Objective

To evaluate the distribution of ABX464 and its main metabolite (N-Glu) in various compartments in HIV-1 Seronegative and Seropositive adult subjects.

### 2.2 Secondary Objectives

To evaluate the safety of ABX464 administered once daily at one dose, alone in HIV-uninfected subjects and in combination with ARTs in HIV-1 infected adult subjects;

To evaluate the systemic and mucosal immunological response to ABX464 in HIV-uninfected and or in HIV-infected adult subjects;

To evaluate the effect of ABX464 on the HIV reservoir cells in HIV-infected adult subjects;

To evaluate the effect of ABX464 on the control of the viral load and the CD4+/CD8+ in HIV-infected adult subjects;

To evaluate the effect of ABX464 on the microbiome in HIV-1 Seronegative and Seropositive adult subjects;

To evaluate the effect of ABX464 on the rectal transcriptome & proteome in HIV-1 Seronegative and Seropositive adult subjects.

## 3 Study Design

### 3.1 Overview

The purpose of the ABX464-005 study is to characterize the systemic and mucosal immunological sequelae associated with exposure to ABX464 and to explore selected immunological endpoints, compartmental pharmacokinetics, and pharmacodynamics. The site will screen and enroll 12 HIV-infected subjects who will receive 150 mg ABX464 orally once daily for 28 days (Cohort 1). Following completion of this cohort a further 24 subjects will be enrolled: 12 HIV-uninfected subjects will receive 50 mg ABX464 orally once daily for 28 days (Cohort 2) and 12 HIV-infected subjects (Cohort 3) will receive 50 mg ABX464 orally once daily for 84 days.

Following screening, eligible subjects in both cohorts will undergo a baseline visit during which blood and tissue samples will be collected. All subjects will have additional blood and tissue samples

collected on Day 28 of dosing (and on Day 84 for subjects enrolled in cohort 3) and four weeks after completion of dosing. The HIV infected subjects should be receiving a stable combination antiretroviral regimen for 12 months and be fully virally suppressed (plasma viral load < 50 copies/mL) during the last 6 months prior to enrolment.

Dose limiting toxicity (DLT) is defined as a grade 3 or higher adverse event as defined by the Division of AIDS table for grading the severity of adult and pediatric adverse events (including signs/symptoms, lab toxicities and/or clinical events) considered by the Data Safety Monitoring Board as probably or definitely related to study treatment.

If more than 2 DLTs occur during the treatment period of the first four treated subjects, then the enrolment of additional subjects will be stopped. In addition, in case of a life threatening (grade 4) adverse reaction enrolment and treatment of ongoing subjects will be immediately discontinued. In both cases, enrolment will only be resumed upon the decision of the sponsor if the Data Safety Monitoring Board can conclude that the causality of the event was unrelated or unlikely related to study treatment.

### 3.2 Inclusion and Exclusion Criteria

To be eligible for inclusion into this study, each patient must fulfil all inclusion criteria and not violate any exclusion criteria (for the protocol under which they are entered) during screening. Details of the inclusion and exclusion criteria are presented in the protocol.

### 3.3 Study Treatment

HIV infected Subjects must be on a stable antiretroviral regimen for 12 months and have a plasma viral load of < 50 copies/mL for at least 6 months prior to enrolment into the study and be willing to continue their antiretroviral regimen for the duration of the ABX464-005 study

12 HIV-infected subjects are screened and enrolled. They receive 150 mg ABX464 orally once daily for 28 days (Cohort 1). Following completion of this cohort a further 24 subjects are to be enrolled: 12 HIV-uninfected subjects receive 50 mg ABX464 orally once daily for 28 days (Cohort 2) and 12 HIV-infected subjects (Cohort 3) who receive 50 mg ABX464 orally once daily for 84 days.

### 3.4 Study Timepoints

From a subject standpoint, the study participation is defined as

- Two to four weeks of screening period;
- Four weeks (Cohorts 1 & 2) or twelve weeks (Cohort 3) as the treatment period (ABX464);
- Follow-up visits at 1 week and 4 weeks after cessation of study medication.

Overall, the minimal study duration is approximately 70 days and up to 140 days depending on the subject Cohort.

Visits and visit windows are defined as follows:

Visit	Study Day	Window
-------	-----------	--------

Screening	-21	± 7 days
Baseline	1	
Control (Cohort 2 only)	7	± 2 days
Control (Cohort 2 only)	14	± 2 days
Control (Cohort 2 only)	21	± 2 days
Day 28 (Cohort 3 only)	28	± 2 days
End of Study Treatment (Cohort 1 & 2)	28	± 2 days
Follow-up (Cohort 1 & 2)	35	± 2 days
End of Study (Cohort 1 & 2)	56	± 7 days
Day 56 (Cohort 3 only)	56	± 2 days
End of Study Treatment (Cohort 3 only)	84	± 2 days
Follow-up (Cohort 3 only)	91	± 2 days
End of Study (Cohort 3 only)	112	± 7 days

### 3.5 Sample Size Considerations

No formal sample size calculations were performed. 36 subjects (24 HIV infected and 12 HIV uninfected subjects) are deemed sufficient to fulfil the study objectives.

### 3.6 Randomization

36 Subjects will be enrolled in this study. These subjects will be enrolled at one site in Spain. No randomizations were performed.

## 4 Study Endpoints

### 4.1 Primary Endpoint

Main pharmacokinetic parameters ( $C_{max}$ , AUC) after first dose of ABX464 (Day 1),

- Cohort 1: at Day 28 and at Day 56 for plasma, PBMC and rectal tissue.
- Cohort 2: at Day 28 and at Day 56 for plasma and PBMC. Rectal tissue only at Day 28.
- Cohort 3: at Day 28, Day 84 and Day 112 for plasma, PBMC and rectal tissue.

### 4.2 Secondary Endpoints

Number and grade of treatment-emergent adverse events, including treatment-emergent serious adverse events, adverse events leading to investigational product discontinuation, during the study;

Change in GALT HIV reservoirs in rectal tissue from Baseline to Day 28 and Day 56 in HIV-infected subjects (Cohort 1) and from Baseline to Day 28, Day 84 and Day 112 (Cohort 3);

Change in total viral DNA in the reservoir cells from Baseline to Day 28 and Day 56 in HIV-infected subjects (Cohort 1) and from Baseline to Day 28, Day 84 and Day 112 (Cohort 3);

Change in inflammatory markers in plasma from Baseline including IL-4, IL-6, IL-8, IL-12, IP-10, G-CSF, IFNg, D-dimer, CRP, sCD14 to Day 28 and Day 56 in subjects enrolled in Cohort 1 & 2 and to Day 28, Day 84 and Day 112 in subjects enrolled in Cohort 3;

Change in immunophenotype and assessment of cell-activation markers from Baseline in PBMCs and MMC, using an 11-colours panel, including: CD3, CD8, CD4, CD45RA, CCR7, CD27, CD28, CD38, HLA-DR, PD-1, viability to Day 28 and Day 56 in subjects enrolled in Cohort 1 & 2 and to Day 28, Day 84 and Day 112 in subjects enrolled in Cohort 3;

Change in HIV-1 RNA, CD4+ and CD8+ counts from Baseline to Day 28 and Day 56 in HIV-infected subjects (Cohort 1) and from Baseline to Day 28, Day 84 and Day 112 (Cohort 3);

Change of rectal microbiota using taxonomic markers from Baseline to Day 28 and Day 56 in subjects enrolled in Cohort 1 & 2 and to Day 28, Day 84 and Day 112 in subjects enrolled in Cohort 3;

Change in the transcriptome & proteome from Baseline to Day 28 and Day 56 in subjects enrolled in Cohort 1 & 2 and to Day 28, Day 84 and Day 112 in subjects enrolled in Cohort 3.

#### 4.3 Pharmacokinetic Endpoint

ABX464 has a very short  $t_{1/2}$  (1 to 2 h) and generally no drug could be quantified after 10h post-dose, so steady-state is virtually reached at the second administration.

NGlcABX464 (main ABX464 metabolite) has a  $t_{1/2}$  of 90 to 110 h, meaning that steady-state is reached after 19 to 22 days of administration.

Pharmacokinetic parameters are assessed in plasma, in PBMC and in rectal mucosa.

Intensive Pharmacokinetic runs are conducted after the first dose of ABX464 (Day 1) and for

② Cohort 1: at Day 28 and at Day 56 for plasma, PBMC and rectal tissue.

② Cohort 2: at Day 28 and at Day 56 for plasma and PBMC. Rectal tissue only at Day 28.

② Cohort 3: at Day 28, Day 84 and Day 112 for plasma, PBMC and rectal tissue.

Following PK parameters will be derived for ABX464 and ABX464-N-glucuronide

- $C_{max}$ ,  $t_{max}$ : the maximum plasma concentration ( $C_{max}$ ) and the time taken to reach  $C_{max}$  ( $t_{max}$ ) will be obtained directly from the concentration-time data.
- $AUC_{0-\tau}$ : the area under the concentration-time curve from time zero to the time of dosing interval  $\tau$  (24 h post-dose for ABX464 and ABX464-N-glucuronide). If no concentration can be measured at this time point,  $AUC_{0-last}$  (from time zero to the last quantifiable concentration)

will be calculated. Both parameters will be presented independently. For both parameters, a linear trapezoidal method will be used.

In addition, five rectal biopsies at each time point will be sent to ALTANBIO for tissue PK determination.

#### 4.4 Safety endpoint

Analysis of safety will be performed on the safety data set consisting in all subjects who received at least one dose of ABX464 in the study. The assessment of safety will be based on the frequency of adverse events (with and without regard to causality) graded according to the Division of AIDS table for grading the severity of adult and pediatric adverse events (Version 2.0 November 2014) and also, the review of individual values for clinical laboratory data, vital signs and ECG focusing on the detection of abnormal values and PCSAs [potentially clinically significant abnormalities (PCSA) determined upon investigator considerations].

Adverse events will be tabulated (counts and percents) by group and dose. All adverse events will be listed and the data will be tabulated by body system/organ class. Adverse event tabulations will include all treatment emergent adverse events, which will be further classified by severity, and relationship to treatment and dose level.

Clinical laboratory parameters, vital signs, ECG will be summarized by using descriptive statistics (n, mean, SD, SEM, median, minimum and maximum). Number of subjects with at least one abnormal values will be tabulated (counts and percents) for each parameter in summary shift tables, by group and dose.

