3. INVESTIGATIONAL PLAN

3.1. Study design

3.1.1. Design and methodology

The ABX464-005 study is a Phase Ib, sequential cohort open label trial designed to provide additional safety and compartmental PK data on ABX464.

The study will also generate exploratory immunological and virological data that combined with the compartmental PK data will help further characterize the mechanism of action of ABX464.

The study will enroll both HIV-infected (N=24) and HIV-uninfected (N=12) study subjects in three distinct cohorts:

- Cohort 1: 12 HIV-infected subjects treated with ABX464 150 mg o.d. for 28 days
- Cohort 2: 12 HIV-uninfected subjects treated with ABX464 50 mg o.d. for 28 days
- Cohort 3: 12 HIV-infected subjects treated with ABX464 50 mg o.d. for 84 days

HIV-infected subjects will add the investigational product to their current antiretroviral regimen whereas the HIV-uninfected subjects will only receive the investigational product.

Cohort 1 will consist of 12 HIV infected subjects. After full enrollment and an interim analysis (including PK and immunological markers) of Cohort 1, Cohort 2 and 3 will begin enrollment and will consist of both HIV infected (n=12) and HIV uninfected (n=12) subjects.

Subjects who successfully complete a screening visit (Visit 1) will advance to a Baseline visit (Visit 2; Day 1). During this visit all subjects will undergo a physical examination and have blood and rectal tissue samples collected.

The rectal tissue samples will be collected before initiating oral dosing with the investigational product (150 mg or 50 mg of ABX464).

After receiving the first dose of ABX464, additional blood PK samples will be collected at 0h, 0.5h, 1h, 1.5h, 2h, 4h, 6h and 8 hours.

All subjects will receive the investigational product once daily for 28 days (Cohorts 1 &2) and for 84 days (Cohort 3).

At Day 28 for subjects enrolled in cohort 3 and at the end of the treatment period (End of Rx Visit; Day 28 for Cohorts 1&2 and Day 84 for Cohort 3) subjects will undergo a physical examination and have blood and rectal tissue collected. PK blood samples will be collected at 0h, 0.5h, 1h, 1.5h, 2h, 4h, 6h and 8 hours.

HIV infected subjects will continue with their antiretroviral regimen i.e. there will be no antiretroviral treatment interruption in this study.

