9.3. Safety Analyses

Adverse events will be coded using the standard dictionary (MedDRA) down to the lower level term (LLT).

An overall summary table will be presented: any adverse event, any treatment emergent adverse event (TEAE), any serious adverse event (SAE), death, any grade 3 or higher adverse events from baseline to EoS.

Two periods will be defined for TEAE:

- Any adverse event which occurs or worsens from first dosing to Day 28;
- Any adverse event which occurs after Day 28.

Adverse events will be described by primary system organ class and preferred term. Numbers and percentage of subjects, and number of occurrence of adverse event will be presented for:

- TEAE;
- Serious TEAE;
- TEAE leading to drug discontinuation;
- TEAE of grade 3 or 4;
- TEAE for which relationship with the study drug is recorded as possible or probable.

The assessment of safety will be based on the frequency of adverse events (with and without regard to causality) graded according to the Division of AIDS table for grading the severity of adult and pediatric adverse events (version 2.0, November 2014) and also, the review of individual values for clinical laboratory data, vital signs and ECG focusing on the detection of abnormal values and PCSAs [potentially clinically significant abnormalities (PCSA) determined upon investigator considerations].

Adverse events will be tabulated (counts and percents) by group. All adverse events will be listed and the data will be tabulated by body system/organ class. Adverse event tabulations will include all treatment emergent adverse events, which will be further classified by severity, and relationship to treatment and dose level.

Clinical laboratory parameters, vital signs, ECG will be summarized by using descriptive statistics (n, mean, SD, SEM, median, minimum and maximum). Number of subjects with at least one abnormal values will be tabulated (counts and percents) for each parameter in summary shift tables, by group and dose.

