## 9 Data

## 10 Statistical Methods

### 10.1 General Principles

All statistical methods will be based on the International Conference on Harmonisation (ICH) E9 document "Statistical Principles for Clinical Trials".

Data will be summarised by cohort. A total column showing all patients will be included for baseline and safety summaries. Where appropriate, data will also be summarised by visit with summaries for each visit attended as scheduled and an additional summary for final (last scheduled visit or early withdrawal). The format of the summaries is defined in the shells in a separate document.

All summary tables will be made up of the following three columns:

- Cohort 1: Hiv infected subjects receiving the 150mg dose of ABX464 for 28 days;
- Cohort 2: Hiv uninfected subjects receiving the 50mg dose of ABX464 for 28 days;
- Cohort 3: Hiv infected subjects receiving the 50mg dose of ABX464 for 84 days.

In addition, summary tables for total DNA will be made up with an additional column of cohort 1 and Cohort 3 pooled.

In summary and analysis tables of continuous variables, standard descriptive statistics (N, mean, standard deviation [SD], median, quartiles, minimum, maximum ) will be presented when relevant. 95% confidence Intervals (CI) will be presented in the statistical analysis outputs as appropriate. For PK summaries, arithmetic mean (AM), geometric mean (GM) and coefficient of variation (%CV) will be used to summarise the data. The minimum and maximum statistics will be presented in summary tables to the same number of significant figures as the original data. The mean/AM, median, GM, CI, SD and will be presented to one more significant than the original data.

For numeric data which includes non-numeric values (e.g. PK data reported as BLQ or lab results reported as < 10 or >100) the following principles will be applied when summarising the data:

- BLQ will be replaced with a value that is ½ of the lower limit of quantification (LLQ)
- Results reported as < x will be treated in the same way as BLQ with LLQ=x
- Otherwise AM, GM, SD, CI and %CV will not be calculated
- Whenever meaningful, minimum, median and maximum will be presented based on the reported data (e.g. minimum = <10, median = 20, maximum = >100)

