### 11.4.1 Adverse Events

All adverse events (AE) will be classified using the version of the MedDRA coding dictionary.

Events will be classified as treatment-emergent if they started or increased in severity on or after the first date and time of medication dosing at Day 1 and up to End of Rx, or withdrawal date if the

patient discontinues before End of Rx. If an event start date is partial, then the start day, month, year or stop date will be used to determine if the event is treatment-emergent. If the classification of the AE cannot be determined from the data available, then the event will be considered treatment-emergent.

Any adverse event which occurs after End of Rx will be classified as post-treatment-emergent.

An overall summary table will be presented using the safety set for adverse events occurring from baseline to the end of the study in the following categories:

- Any adverse event;
- Any treatment-emergent adverse event (TEAE);
- Any post-treatment-emergent adverse event;
- Any serious adverse event;
- Any severe adverse event (Common Toxicity Criteria [CTC] grade 3 or 4);
- Death

TEAEs will be further classified and summarised as follows:

**Severe TEAEs:** Severity classified as 'Grade 3', 'Grade 4' or missing.

**Serious TEAEs:** Seriousness classified as 'yes' or missing.

**Drug-related TEAEs:** Relationship to study drug classified as 'yes' or missing.

**Serious drug-related TEAEs:** Both serious and drug-related, as specified above.

**TEAEs leading to study drug discontinuation:** Action taken classified as 'permanent discontinuation'.

Summaries by system organ class (SOC) and preferred term (PT) will also be presented for treatment-emergent events. Similar tables will be presented for each of the classifications of treatment-emergent events above.

A summary of the mean duration (days) of treatment-emergent events will also be presented by SOC and PT, along with the number of events. Duration of an event is calculated as (stop date of event - start date of event) + 1. If an AE is ongoing then use the end of study date (or last known visit date for early termination) as the stop date.

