All AE summary tables, unless otherwise specified, will show the number (%) of patients having at least one event and the number of events in each treatment group and overall. Note: If a patient has multiple AEs with the same preferred term, these will be summarised once within the count for N (%) of patients, but each event will be counted within the number of reports E of each AE. Changes in severity of the same AE (if collected) will be counted only once within the number of reports E of each AE.

All adverse events recorded on the CRF will be listed by SOC and PT within the data listings.

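### SAP 11.4.1 counts treatment-emergent events over 28 days in Cohorts 1 and 2 but 84 days in Cohort 3, and omits the common Day 28 period of protocol 9.3

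*SAP*

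**What the plan says.** Protocol 3.1.1 and SAP 10.1 define three cohorts of 12, each with one dose and one duration. Cohort 1 (HIV-infected) takes 150 mg and Cohort 2 (HIV-uninfected) takes 50 mg, both over 28 days. The third has a longer course: "Cohort 3: Hiv infected subjects receiving the 50mg dose of ABX464 for 84 days".

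SAP 11.4.1 treats an event as treatment-emergent if it starts or worsens "on or after the first date and time of medication dosing at Day 1 and up to End of Rx" (or up to withdrawal, if earlier). Anything later is labelled post-treatment-emergent. The same section says the AE tables "will show the number (%) of patients having at least one event and the number of events in each treatment group and overall". SAP 4.4 states: "Adverse events will be tabulated (counts and percents) by group and dose". SAP 10.1 adds a total column to the safety summaries.

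Protocol 9.3 divides treatment-emergent events differently. Its first period is "Any adverse event which occurs or worsens from first dosing to Day 28" and its second is everything after Day 28. The SAP has no cut at Day 28. SAP 11.5 derives days of exposure and summarises them, but no AE table uses them.

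**The concern.** Number and grade of treatment-emergent events is the first-listed secondary endpoint. Cohort 1 against Cohort 3 is the only place where 150 mg and 50 mg can be set side by side in HIV-infected subjects on antiretroviral therapy. Cohort 1 against Cohort 2 has equal duration, but the two differ in HIV status and background therapy as well as dose.

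In the Cohort 1 and Cohort 3 columns the lower dose is watched three times as long. A subject has more time to have a first event, and more events accumulate, whatever the dose does. A reader of the planned tables could see a lower percent at 150 mg and take the higher dose to be at least as well tolerated, when the gap comes from the window. Day 1–28 incidence cannot be recovered from a Day 1–84 percent. The total column has the same mixture, because it adds 28-day and 84-day subjects under one denominator.

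**Working it through.** The plan has no figure to reproduce: both documents say no formal sample size calculation was done, and neither gives an expected AE rate.

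**Inputs from the documents.** 12 subjects per cohort; windows of 28, 28 and 84 days (SAP 10.1, 11.4.1).

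- Window ratio, Cohort 3 to Cohort 1: 84/28 = 3.0.
- Planned subject-days: Cohort 1, 12×28 = 336; Cohort 2, 12×28 = 336; Cohort 3, 12×84 = 1008.
- Total column: 336+336+1008 = 1680, of which Cohort 3 supplies 1008/1680 = 60% from one third of the subjects.

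**Assumed inputs.** p = 28-day risk of at least one event at 50 mg in HIV-infected subjects; HR = true hazard ratio, 150 versus 50 mg; f = average hazard after Day 28 divided by average hazard up to Day 28.

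**Model.** Let H = −ln(1−p) be the cumulative hazard over 28 days at 50 mg.

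- Cohort 1 over 28 days: HR×H, so the risk is 1−(1−p)^HR.
- Cohort 3 over 84 days: H + (56/28)×f×H = (1+2f)×H, so the risk is 1−(1−p)^(1+2f).

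The two columns agree when HR = 1+2f, whatever p is. For 1 < HR < 1+2f the 150 mg column is lower although its hazard is higher. The same break-even holds for event counts, with HR read as a rate ratio.

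**Results at p = 20%.**

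| f | Cohort 3, Day 1–84 | Break-even HR |
|---|---|---|
| 1 | 1−0.8^3 = 48.8% | 3.0 |
| 0.5 | 1−0.8^2 = 36.0% | 2.0 |
| 0.25 | 1−0.8^1.5 = 28.4% | 1.5 |
| 0 | 20.0% | 1.0 (no artefact) |

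Cohort 1 shows 20.0% at HR 1, 28.4% at HR 1.5, 36.0% at HR 2 and 48.8% at HR 3.

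**No dose effect, f = 1.** Risks of 10%, 20% and 30% in Cohort 1 stand beside 27.1%, 48.8% and 65.7% in Cohort 3. At 30% that is 12×0.30 = 3.6 subjects against 12×0.657 = 7.9.

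**With a common Day 28 window.** At p = 20%, HR = 2 and f = 1, the SAP window gives 36.0% (Cohort 1) against 48.8% (Cohort 3); the first 28 days give 36.0% against 20.0%. With exact binomials and 12 per cohort, the chance that Cohort 3 shows more affected subjects than Cohort 1 falls from 67% to 13%.

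**Person-time as an alternative.** Suppose f = 0 and the doses are equally tolerated. Both cohorts then expect the same number of events, but over 336 and 1008 subject-days. The crude rate in Cohort 3 would be one third of that in Cohort 1. Events per subject-time therefore mislead in the opposite direction if events cluster early.

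**The case against.** The strongest reply is that the SAP plans no dose comparison for safety. There is no test or between-cohort estimate. The safety objective refers to one dose, given alone or with antiretroviral therapy. The cohorts are sequential and non-randomised. This stands: a reader might infer that a formal 150 versus 50 mg analysis is biased, and none exists. But the descriptive columns are the planned safety evidence, and SAP 4.4 asks for them by dose.

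A reader might also infer from SAP 4.4 that the 28-day and 84-day 50 mg subjects will be pooled into one column. The documents do not support that. SAP 10.1 fixes one column per cohort, and each cohort has one dose. The only extra pooled column named joins Cohorts 1 and 3, for total DNA. Only the total column clearly mixes windows in the AE tables.

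The durations are disclosed in the cohort definitions and all events are listed. The table shells are a separate document, so a period split there cannot be excluded. Disclosure helps a careful reader but does not supply the missing Day 28 figure, and the SAP text does not ask for one.

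Precision is poor in any case: 4 of 12 and 8 of 12 have exact 95% intervals of about 10–65% and 35–90%. That limits what any table can show, but it does not justify adding a distortion that can be avoided.

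**Conclusion.** The point holds as a mismatch between SAP 11.4.1 and protocol 9.3 that leaves the HIV-infected 150 mg and 50 mg columns on unequal windows. The threefold ratio and the missing common period come straight from the documents. The effect on the percents does not: it depends on f, which is unknown. The break-even hazard ratio runs from 1.0 (f=0) through 1.5 and 2.0 to 3.0 (f=1), and would exceed 3.0 only if the hazard rose after Day 28.

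It would be too strong to say that the lower dose will look worse, or that any hazard ratio below 3 is reversed; both need a constant hazard, for which the documents give no evidence. The supported statement is that the crude contrast is distorted unless no new events start after Day 28. This should be corrected before the tables are produced, but it does not threaten the primary pharmacokinetic endpoint.

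**What to change.** In SAP 11.4.1, reconcile the treatment-emergent periods with protocol 9.3:

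1. Make the between-cohort tables, including the total column, cover events with onset or worsening from first dose to Day 28 in all three cohorts, using study day as defined in SAP section 5. State that the grade shown is the highest reached by Day 28, because SAP 10.1 otherwise collapses later worsening into the same event.
2. Show Cohort 3 from Day 29 to End of Rx separately. The protocol's period after Day 28 should not be one row across cohorts, since Cohort 3 is then on drug and Cohorts 1 and 2 are off it.
3. Optionally, add events per subject-time to the overall summary only, using the exposure days from SAP 11.5. Note that this assumes a roughly constant hazard and would favour Cohort 3 if events cluster early. It should not be extended to the organ-class and preferred-term tables, where rates from 12 subjects would be unstable.

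The cost is a paragraph of SAP text and slightly longer safety tables. Start dates are already recorded for every event (protocol 8.5), so no new data are needed and no study procedure changes.
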